6 GENERAL ISSUES FOR STATISTICAL ANALYSIS

6.1 ANALYSIS SOFTWARE AND GENERAL METHODS OF ANALYSIS

We will use SPSS (version 27, IL, USA) for all analyses. Two-sided P-values < 0.05 will be considered statistically significant.

- *Primary outcome:* Number of ovulatory cycles
 - The primary outcome was considered a Poisson distributed variable. Thus, we will fit a generalised linear model (GLM) with the Poisson distributional family and a log link function.
- Secondary efficacy outcomes:
 - Continuous outcomes: We will fit mixed-effects linear models (random intercept models). In the fixed-effects parts of the models, we will include group (1 = obesity surgery, 0 = medical care) and time as a continuous outcome. Number of reported menses within the 52-week follow-up period: We will use an identical approach compared to the primary outcome, namely a Poisson regression model via GLM and bootstrap Student's t test.
- *Secondary safety outcomes:* Safety outcomes will be evaluated via Fisher's exact tests at 52 weeks.

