 - Reproductive profile: serum luteinizing hormone (LH), follicle-stimulating hormone (FSH), oestradiol, sex hormone binding globulin (SHBG), testosterone, dehydroepiandrosterone sulphate (DHEAS) and androstenedione.
 - o Urine pregnancy test
- Every 6 months: OGTT, Anti-mullerian hormone (AMH), modified Ferriman Gallwey score, Ludwig visual score and Savin Alopecia Scale), Hospital Anxiety and Depression Scale (HADS), Multidimensional Health Profile: Health Functioning questionnaire (MHP-H), Social Functioning Questionnaire (SFQ), PCOS Health-Related Quality of Life, and Cardiff Acne Disability Index questionnaires, blood pressure, plasma lipids, liver function tests and HbA1c.

Sub-studies follow-up

All participants will be given the opportunity to take part in state-of-the-art studies that will investigate the physiological mechanisms underpinning the clinical impact of the two treatments (Appendix 2). These will be performed at the following time points:

- Energy expenditure and sleep-disordered breathing: baseline and 6 months
- Endometrial clonal activity : baseline and 6 months
- Adipose tissue biology: baseline and 6 months
- Functional Magnetic Resonance Imaging (fMRI): baseline and 3 months

Contraception

Participants will be asked to maintain effective contraception for the duration of the study. Effective contraception methods include:

- Barrier methods
- intrauterine device (non-hormone releasing)

- vasectomised partner: this is a highly effective birth control method provided that partner is the sole sexual partner of the trial participant and that the vasectomised partner has received medical assessment of the surgical success.
- sexual abstinence: sexual abstinence is considered a highly effective method only if defined as refraining from heterosexual intercourse during the entire period of risk associated with the study treatments and when this is in line with the preferred and usual lifestyle of the subject. Periodic abstinence (e.g., calendar, ovulation, symptothermal, post-ovulation methods), declaration of abstinence for the duration of a trial, and withdrawal are not acceptable methods of contraception.

Drop-outs

Subjects will be free to withdraw at any point. In view of the unprecedented impact of the COVID19 pandemic on clinical research, only participants who withdraw because of fears of contracting the virus will be replaced.

Trial Closure

The end of the clinical trial is defined as the last visit of the last patient.

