GLM	Generalised linear model
CSR	Clinical study report
SAE	Serious Adverse Event
TEAE	Treatment emergent adverse event
AE	Adverse Event
SOC	System organs class
РТ	Preferred Term
CRF	Case Report Form

STUDY DESIGN

This is an open-label randomised-controlled clinical trial to investigate the safety and efficacy of obesity surgery vs medical care for women with polycystic ovary syndrome (PCOS), obesity and oligo- or amenorrhoea.

Patients will be randomised at a ratio of 1:1, stratified by body mass index (BMI) and trial site to:

- Medical care: a combination of lifestyle modification and pharmacotherapy or
- Obesity surgery: standard laparoscopic vertical sleeve gastrectomy (VSG).

Key Inclusion criteria

- Pre-menopausal women ≥ 18 years old
- BMI \ge 35 kg/m² with obesity-related complications
- Diagnosis of PCOS based on international evidence-based guidelines for the assessment and management of PCOS 2018

Key Exclusion criteria

- Type 1 or Type 2 diabetes mellitus
- Specific contraindications to obesity surgery
- Previous obesity surgery
- Inability to maintain adequate contraception
- Medications affecting reproductive function (e.g. oral steroids, hormonal contraceptives) at screening or 3 months previously.
- Other causes of anovulation (e.g. untreated hypothyroidism, adrenal or pituitary disorders)
- Current pregnancy or breastfeeding

Key outcomes

Reproductive

- Weekly serum progesterone
- Monthly profile of reproductive hormones
- Self-reported menses

Metabolic

- Oral glucose tolerance test measuring glucose and insulin secretion and sensitivity indices. This will take place pre-intervention, at 26 weeks and 52 weeks post-intervention.
- Monthly metabolic profile: fasting glucose, insulin, and HOMA-IR.

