8.2 SECONDARY EFFICACY OUTCOMES

• Number of reported menses within the 52-week follow-up period: We will use an identical approach compared to the primary outcome, namely a Poisson regression model via GLM and bootstrap Student's t test.

The following secondary efficacy outcomes will be compared between treatment groups using a mixed-effects regression modelling:

- Anthropometric measurements body composition, waist circumference, body weight
- Metabolic outcomes glycated plasma haemoglobin (HbA1c), plasma liver function tests, plasma lipid profile
- Arterial blood pressure
- Reproductive hormones serum luteinising hormone (LH), follicle-stimulating hormone (FSH), oestradiol, sex hormone binding globulin (SHBG), testosterone, free androgen index (FAI), dehydroepiandrosterone sulfate (DHEAS), androstenedione, Anti Mullerian hormone (AMH)
- Number of reported menses
- Glucose concentrations at the oral glucose tolerance test (OGTT)
- Hospital Anxiety and Depression Scale (HADS) score
- Multidimensional Health Profile: Health Functioning questionnaire score
- PCOS Health-Related Quality of Life score

- Modified Ferriam-Galwey hirsutism score
- Ludwig visual score
- Savin alopecia scale score
- Cardiff Acne Disability index
- Number of medications

We will fit mixed-effects linear models (random intercept models). In the fixed-effects parts of the models, we will include group (1 = obesity surgery, 0 = medical care) and time as a continuous outcome. We will use likelihood ratio tests to determine if there is an improvement in the model fit when including a treatment-by-time interaction, as evaluated using the Akaike information criterion. We will use a cutoff of a difference greater than 2 in AIC to indicate a significant improvement in the model.

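### The random-intercept-only mixed models understate the treatment-by-time standard error if women's rates of change vary within an arm: possibly severely with 13 monthly visits, by at most a factor of 1.41 with three

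*SAP*

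**What the plan says.** SAP 6.1 and 8.2 give the same model for the continuous secondary outcomes: "We will fit mixed-effects linear models (random intercept models". For the fixed effects, "we will include group (1 = obesity surgery, 0 = medical care) and time as a continuous outcome". SAP 8.2 makes the interaction conditional: "We will use likelihood ratio tests to determine if there is an improvement in the model fit when including a treatment-by-time interaction", with the rule "We will use a cutoff of a difference greater than 2 in AIC to indicate a significant improvement in the model". SAP 6.1 also applies a general threshold to all analyses: "Two-sided P-values < 0.05 will be considered statistically significant".

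Neither document states a random slope, a residual correlation structure, a robust standard error or a degrees-of-freedom method. Protocol section 7 names ANCOVA and chi-square tests, so it supplies no covariance structure either.

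On visit frequency, the SAP's key outcomes include "Monthly profile of reproductive hormones". Protocol section 6 puts the reproductive profile under monthly assessments. Appendix 1 also lists body weight and number of medications at baseline and at each of 12 months, which makes 13 time points. OGTT, AMH, lipids, liver tests, HbA1c, blood pressure, questionnaires and the hirsutism and alopecia scores are six-monthly, which makes three time points.

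**The concern.** A random intercept lets women start at different levels but makes all women in an arm change at the same rate. It implies the same correlation between any two visits, however far apart. If rates of change really differ, the model has nowhere to put that variation except the visit-level residuals, which it treats as independent. Thirteen visits on one woman then count as nearly independent evidence on the slope, although the uncertainty about an arm's mean slope is limited by the number of women.

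The treatment-by-time term carries the treatment effect on change over time. If its standard error is too small, intervals are too narrow and p-values too low. The AIC step uses the same likelihood, so it offers no protection.

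The documents make a single common slope hard to believe for weight. Medical care is personalised with optional drugs (Protocol section 6), the background section reports regain in more than 80% of patients after lifestyle weight loss, and clinicians may give alternative treatment while the woman stays in the analysis (Protocol 8.2).

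**Working it through.** **No figure in the plan to reproduce.** The documents give no slope variance, residual variance or power for any mixed-model outcome. The only sample size calculation, 33 per arm, concerns the primary outcome and is not in question.

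**Inputs from the documents.** n = 40 per arm (SAP section 4). Visits: m = 13 at months 0 to 12, or m = 3 at months 0, 6 and 12. Sxx, the sum of squared deviations of visit times from their mean, is 2 × (1+4+9+16+25+36) = 182 for 13 visits and 36+0+36 = 72 for three.

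**Assumed inputs.** Slopes vary between women with SD τ per month, so true 12-month change has SD 12τ. The residual SD is s. Define r = 12τ/s. As an illustration for weight, an SD of 12-month change of 4 to 10 kg and a residual SD of 2 to 3 kg give r from 4/3 = 1.33 to 10/2 = 5.

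**Closed form, complete data.**
- True variance of the slope difference: 2(τ² + s²/Sxx)/n.
- Variance reported by the random-intercept model: 2(s² + τ²Sxx/(m−1))/(n·Sxx), because slope variation inflates the pooled residual.
- True/reported SE = √[(τ² + s²/Sxx) / (τ²/(m−1) + s²/Sxx)]. The number of women cancels, and the limit for large r is √(m−1).

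Multiplying through by 144/s² gives, for 13 visits (144/182 = 0.791), ratio² = (r² + 0.791)/(r²/12 + 0.791). For three visits (144/72 = 2), ratio² = (r² + 2)/(r²/2 + 2).

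Example, 13 visits and r = 1: 1.791/0.8745 = 2.048, so the ratio is 1.43. The type I error of a nominal 5% test is 2[1 − Φ(1.96/ratio)] = 2[1 − Φ(1.37)], about 17%.

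**AIC rule.** One added parameter lowers AIC by LR − 2, where LR is the likelihood ratio statistic. A drop of more than 2 therefore means LR > 4, a nominal p below 0.0455.

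**Results under no treatment effect** (simulation: 40 per arm, complete data, 6,000 runs per setting):

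| r | 13 visits: SE ratio | type I error, simulated | AIC rule keeps interaction | 3 visits: SE ratio | type I error, simulated | AIC rule keeps interaction |
|---|---|---|---|---|---|---|
| 0 | 1.00 | 5.7% | 5.4% | 1.00 | 5.1% | 4.9% |
| 0.5 | 1.13 | 8.3% | 7.7% | 1.03 | 5.4% | 5.0% |
| 1 | 1.43 | 17% | 17% | 1.10 | 7.6% | 7.3% |
| 2 | 2.06 | 34% | 33% | 1.22 | 12% | 11% |
| 3 | 2.52 | 44% | 43% | 1.30 | 14% | 13% |
| 5 | 3.00 | 52% | 51% | 1.36 | 14% | 14% |
| limit | 3.46 | – | – | 1.41 | about 17% (closed form) | – |

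For the weight illustration (r = 1.33 to 5), the closed form gives an SE ratio of 1.65 to 3.00 and type I error of 24% to 51% with 13 visits. With three visits it gives 1.14 to 1.36 and 9% to 15%.

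**Does categorical time cure it?** Take the difference between arms in change from baseline to month 12. In units of s², the true variance per woman is r² + 2. The random-intercept model reports 2(1 + r²·Sxx/(144(m−1))), which for 13 visits is 2 + 0.2107r². At r = 1.33, 3.778/2.375 = 1.591, ratio 1.26 and type I error 12%. At r = 5, 27/7.267 = 3.716, ratio 1.93 and type I error 31%. The error is smaller but remains.

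**After the fix.** With between-woman slope variation in the analysis (a t-test on per-woman slopes, equivalent to a random slope in balanced data), simulated type I error was 4.5% to 5.9% in every setting.

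**The case against.** The strongest reply is that the size rests on a quantity the documents do not give. That stands: at r of 0.5 or less the effect is slight. A reader might infer that standard errors are far too small across all the secondary outcomes. The documents do not support that, for these reasons:

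- Most listed outcomes are six-monthly, where the factor cannot exceed 1.41.
- The kilogram illustration does not carry over to hormones. Women take medroxyprogesterone before baseline so that all are studied at the same cycle phase, but no such alignment is stated for the monthly samples. Visit-to-visit noise may be large, r low and the effect small.
- The SAP never says that all 13 visits enter the model. SAP 2.2.1 names 52 weeks as the main time point, with 26 weeks and baseline also presented. If only those are modelled, the three-visit figures apply. The monthly hormone profile and the reference to temporal changes in SAP 3.2.2 make the 13-visit reading plausible but not certain.
- If the AIC rule drops the interaction, inference rests on the group main effect. With complete data this compares women's means, and no understatement has been shown for it.

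A reader might also infer that the missing-at-random statement in SAP 6.3 fails. Likelihood inference under that assumption does rely on a suitable covariance model, but no size has been put on this.

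Finally, SAP 6.5 calls all secondary outcomes exploratory. That limits the consequence. It does not make an interval correct, and SAP 6.1 still applies the 0.05 threshold to all analyses. For weight, a false positive is perhaps the least worrying result, since the protocol cites losses of 25–30% after surgery; the interval would still be too narrow.

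**Conclusion.** The point holds conditionally. If rates of change vary between women within an arm, the model as written understates the treatment-by-time standard error, and nothing else in the SAP corrects this. If all 13 monthly visits are modelled, the factor runs from about 1.1 at r = 0.5 to 3.0 at r = 5, with a ceiling near 3.5. With three visits the ceiling is 1.41. The AIC rule is triggered too often by almost the same margin.

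The mechanism is certain; the magnitude is not, because r is assumed and the calculations use complete data. Body weight is the plausible severe case, and noisy hormones may be little affected.

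The primary Poisson analysis, the Poisson model for menses and the Fisher tests are untouched, so no confirmatory conclusion depends on this. The SAP should be changed, but the point does not threaten the trial's main result.

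**What to change.** In SAP 6.1 and 8.2, replace the random-intercept specification with:

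- **Outcomes at baseline, 26 and 52 weeks:** an unstructured residual covariance across the three visits.
- **Monthly outcomes:** a random intercept and a random slope for time, with unstructured covariance between them.
- **Both:** Satterthwaite degrees of freedom, and a named simpler structure as fallback if the model does not converge.

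The SAP should also state which visits enter the model for each outcome, since the size of the problem turns on this. Any step that decides on the interaction should use the revised covariance.

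The cost is SAP wording, somewhat wider intervals and possible convergence handling. The models are available in SPSS MIXED, so the planned software need not change.

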6.2 DISPOSITION OF SUBJECTS AND WITHDRAWALS

All subjects who provide written informed consent will be accounted for. The number and percentage of ITT subjects who discontinued the study prior to Week 52 will be presented by treatment group, overall and by reason of discontinuation (adverse event, discontinued by investigator, withdrawn consent/request to terminate, lost-to-follow-up, death, other). Percentages will be based on the number of ITT subjects.

6.3 METHODS FOR MISSING DATA

All efforts will be made to prevent the occurrence of missing data. Nevertheless, it is anticipated that withdrawals will occur and hence there will be missing data on primary and secondary efficacy endpoints. As outlined above, we will use Poisson regression, incorporating all available data, even for participants lost to follow-up. In addition, we will use mixed-effects modelling, which naturally accounts for missing data assuming that data are missing at random. The number of participants with missing data per variable and reasons will be reported as recommended[3].

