3.2 Study Endpoints

3.2.1 PRIMARY EFFICACY ENDPOINT

Primary efficacy outcome:

Number of ovulatory cycles within the 52-week follow-up period. Ovulation will be defined as a rise in serum progesterone ≥ 16 nmol/L.

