5 ANALYSIS POPULATIONS

5.1 INTENTION TO TREAT POPULATION (ITT)

We will recruit 80 women, with each group comprising forty participants randomised at a 1:1 ratio. The intention-to-treat (ITT) population will include all patients who were initially assigned to either medical care or obesity surgery, regardless of any deviations from the trial protocol or the actual treatment they received. The analysis of this population will be based on their original assignment group.

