8 EFFICACY ANALYSES

8.1 PRIMARY OUTCOME

Number of ovulatory cycles

We will fit a GLM with the Poisson distributional family and a log link function. The Poisson model will be the primary analysis. Results will be presented as incidence rates and incidence rate ratios (95% confidence interval). Standard techniques will be employed to verify the model assumptions, which include residual analysis, overdispersion testing, and influence diagnostics. In case of substantial overdispersion, we may utilise a negative binomial model. As a sensitivity analysis, we will conduct a bootstrap t-test for independent samples. The analysis will include all participants who have complete follow-up data. We will use bias-corrected and accelerated (BCa) intervals via 10.000 replicates.

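### The SAP specifies no exposure offset for the primary Poisson model but keeps women lost to follow-up in it, so the rate ratio is scaled by the ratio of mean follow-up between arms

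*SAP*

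**What the plan says.** The primary endpoint (SAP 3.2.1) is a count over a fixed window: "Number of ovulatory cycles within the 52-week follow-up period". SAP 8.1 gives the model: "We will fit a GLM with the Poisson distributional family and a log link function". SAP 6.1 says the same. Neither section lists the terms of the model, and nowhere does the SAP or protocol mention an offset, person-time, or any scaling or imputation of a partial-year count.

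SAP 6.3 expects withdrawals and missing primary data. For the primary outcome its answer is the Poisson model itself: "As outlined above, we will use Poisson regression, incorporating all available data, even for participants lost to follow-up". SAP 5.1 defines the ITT population as everyone assigned, "regardless of any deviations from the trial protocol or the actual treatment they received".

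On reporting, SAP 8.1 states: "Results will be presented as incidence rates and incidence rate ratios (95% confidence interval". It defines no denominator for those rates. The same section says "The analysis will include all participants who have complete follow-up data". That sentence stands between the one introducing the bootstrap t-test and the one on its BCa intervals, and it does not name the analysis it governs.

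SAP 4 and protocol section 7 allow for 15-20% drop-out overall, with no breakdown by arm or by time. SAP 8.2 applies the primary-outcome approach to the number of reported menses.

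**The concern.** A Poisson model uses incomplete follow-up correctly only if it knows how long each woman was observed. Without that, a woman with 3 ovulations who leaves at week 13 enters as 3 ovulations in 52 weeks, although her observed rate is 3 × 52/13 = 12 per 52 weeks. A missed weekly progesterone sample is likewise treated as a week without ovulation.

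The arm with less observed time then appears to ovulate less. In an open-label comparison of surgery with medical care, observed time could differ by arm. If it does, the primary estimate is biased in a direction that cannot be known in advance, and the test of no difference loses its nominal error rate. Even when the arms lose the same amount of time, the reported rates are too low, and the varying follow-up adds spread that the Poisson standard error ignores.

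**Working it through.** **Inputs from the documents.** Means 7 (medical) and 10 (surgery), SD 3.3, 33 per group for 95% power, 40 recruited per group, 15-20% drop-out (SAP 4); two-sided 0.05 (SAP 6.1). True ratio under the design assumption: 10/7 = 1.43.

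**The plan's own figure.** A two-sample t-test for a difference of 3 with SD 3.3 has 94.7% power at 32 per group and 95.3% at 33, so 33 reproduces. At 15-20% loss, 0.15 × 40 = 6 to 0.20 × 40 = 8 women per arm would contribute a partial-year count.

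**Bias formula.** In a two-group log-link Poisson model without an offset, the fitted ratio is the ratio of mean counts. With a constant rate and non-informative dropout:

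fitted ratio = true ratio × (mean follow-up fraction, surgery) / (mean follow-up fraction, medical).

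If a fraction d leaves at times uniform over the year, the mean follow-up fraction is 1 − d/2 (the same as if all left at 26 weeks).

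**Size of the bias.** The splits by arm are assumptions.

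| Loss, medical v surgery | Factor | True 1 becomes | True 1.43 becomes |
|---|---|---|---|
| 17.5% v 17.5% | 0.9125/0.9125 = 1.00 | 1.00 | 1.43 |
| 20% v 15% | 0.925/0.900 = 1.03 | 1.03 | 1.47 |
| 25% v 10% | 0.950/0.875 = 1.09 | 1.09 | 1.55 |
| 30% v 5% | 0.975/0.850 = 1.15 | 1.15 | 1.64 |
| 10% v 25% | 0.875/0.950 = 0.92 | 0.92 | 1.32 |

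With equal 17.5% loss the fitted means fall to 7 × 0.9125 = 6.4 and 10 × 0.9125 = 9.1, about 9% too low. Equal proportions are not enough if timing differs: 17.5% in each arm, leaving at 13 weeks in medical care and 39 weeks in surgery, gives (1 − 0.175 × 0.25)/(1 − 0.175 × 0.75) = 0.956/0.869 = 1.10.

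**Type I error, missing offset alone.** This was simulated with 40 per arm, mean 7 in both arms, exactly Poisson counts, uniform exit times and the model-based standard error. Without an offset it is about 10-11% at 20% v 15%, 20% at 25% v 10% and 36% at 30% v 5%. With the offset it is about 5% in each. If instead fixed numbers all leave at exactly 26 weeks, the first two fall to about 6% and 15%.

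**Overdispersion, kept apart.** An SD of 3.3 gives a variance of 10.89, which is 10.89/7 = 1.56 times the medical-care mean. With gamma-Poisson counts of that variance, the model-based standard error gives about 12% type I error with no dropout at all. At 25% v 10% loss:

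| Model | Type I error |
|---|---|
| No offset, model-based SE | about 24-25% |
| No offset, robust SE | about 11% |
| Offset, model-based SE | about 11% |
| Offset, robust SE | about 6% |

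Each remedy removes part of the inflation, and only the two together bring it near 5%. Under equal loss, a robust standard error without an offset already gives about 5.5-6%.

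**The case against.** The strongest reply is that the SAP is silent on an offset and does not rule one out. The model terms are not listed at all, not even treatment group, and the promise of incidence rates fits an intention to use person-time. This stands as far as it goes. A reader might infer that the SAP decided against an offset, or that no rate could come from its model. The documents support neither: for a woman followed for 52 weeks the fitted mean is a rate per 52 weeks. But a rate needs a stated denominator, and SAP 6.3 relies on this model to handle dropouts, so the term that would make it do so has to be written down.

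Second, nothing in the documents shows that loss will differ by arm. The protocol plans support groups, aimed particularly at women who wait 12 months without surgery, keeps surgery open to the medical-care group after the trial, and pays £400 on completion. At the two ends of the planned range, 20% v 15%, the bias is only about 3%. This also stands, and the larger scenarios are illustrations. The attention to retention in the non-surgical group does show that the risk was seen as specific to that arm.

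Third, SAP 8.1 tests for overdispersion and allows a negative binomial model. That addresses the variance, though only as an option, and it does not remove the bias in the ratio.

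A reader might also infer that the complete-follow-up sentence contradicts SAP 6.3 and the ITT definition. Its position points to the bootstrap t-test, and on that reading there is no contradiction. What remains is an ambiguity, and a sensitivity analysis that leaves out the very women whose handling it should test.

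**Conclusion.** The point holds as a gap in the specification of the primary analysis with a definite consequence: applied as written, the model multiplies the rate ratio by the ratio of mean follow-up. The factor is exact under a constant rate and non-informative dropout. Its size rests on loss by arm and timing, which the documents do not give: about 3% for a 5-point difference in loss, 9% for 15 points and 15% for 25 points, in either direction.

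It would be tempting to attribute type I errors of 24-38% to the missing offset. Those figures apply to overdispersed counts with a model-based standard error and mix two problems. The offset's own share is better read from the exactly Poisson results, and at 20% v 15% most of that excess is unmodelled spread in follow-up, since equal 17.5% loss already gives about 9-10%. The change is nonetheless worth making before the data are analysed, because it concerns the primary estimate and the choice should not be left open until follow-up by arm is known.

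**What to change.** - **Primary model (SAP 6.1 and 8.1).** Add an offset of ln(weeks with an evaluable progesterone result). Fit the model to all randomised women with at least one evaluable week, using a robust standard error or a negative binomial model with the same offset. State that a week without a result adds nothing to exposure, and report women with no evaluable week by arm.
- **Sensitivity analysis (SAP 8.1).** State that the complete-follow-up sentence governs only the bootstrap t-test, and replace the restriction by running that test on each woman's rate per 52 evaluable weeks, for the same women as the primary model.
- **Reported menses (SAP 8.2).** Use the analogous offset, ln(observed diary weeks).
- **Missing data (SAP 6.3).** State the assumptions of a roughly constant ovulation rate and non-informative dropout. Plan a check of the rate over follow-up time and a sensitivity analysis that departs from non-informative dropout.

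The cost is a few lines of SAP text and one derived variable per outcome, from weekly progesterone and diary data already being collected. The downside is the offset's own assumption: if ovulation changes over the year after treatment, an early leaver's rate does not represent 52 weeks, and if leaving depends on response the offset does not remove the bias. How to treat time after conception is a separate estimand choice and is not part of this change.
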